Both the frequency of WP use and the manner with which it is smoked contributes to the development and maintenance of nicotine dependence.⁹⁻¹¹ WP smoking delivers pharmacologically active doses of nicotine to the user.^{12,13} Although most WP smokers in the U.S. smoke WP intermittently, some eventually move on to more frequent use.^{14,15} **If flavorings are determined to influence users to initially try WP, improve their perceived satisfaction from use of the product, and/or make it more palatable to puff more frequently or take longer/deeper puffs, then they would be contributing to the initiation and maintenance of WP dependence.** Moreover, current level of WP dependence may moderate the impact of flavorings on smoking patterns. Unflavored WP tobacco is more difficult to find and purchase, and internet customer reviews suggest that few WP users try and even fewer continue to use unflavored tobacco (“didn’t taste good”, “may be a little hard for less experienced smokers”); however, some product reviews from WP aficionados are more positive (“This is a blend to be sipped and enjoyed slowly”), suggesting that current WP dependence level may be an important factor in the role of flavors.¹⁶

The overall aim of the current study is to determine if flavorings contribute to the initiation and maintenance (i.e., abuse liability) of WP smoking and also influence how a WP is smoked (i.e., smoking topography), which has implications for both risk of dependence but also smokers’ level of exposure to tobacco-related toxicants. Using a randomized crossover-design, 76 current WP smokers (38 low dependent, 38 high dependent) will complete four counterbalanced WP smoking sessions (preferred flavored-sweetened, preferred flavored-very low sweetened, unflavored-sweetened, unflavored-very low sweetened) that are preceded by 12 hours of tobacco/nicotine abstinence. Sessions will be separated by a standard 48-hour washout period.

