Aim 1: To understand how flavorings impacts WP initiation, smoking behaviors, abuse liability, and exposure to tobacco-related toxicants. (H1a) *Flavored-sweetened WP tobacco will be associated with longer and more frequent puffing resulting in the greatest overall levels of smoke inhalation (mL of smoke inhaled), (H1b) highest abuse potential, and (H1c) greatest levels of exposure to nicotine and carbon monoxide (CO), followed by unflavored-sweetened WP, then flavored-very low sweetened and lastly unflavored-very low sweetened WP.* (H1d) *A majority of WP smokers will report having initiated WP smoking with flavoredsweetened tobacco and report flavoring as an important reason for trying WP.*

Aim 2: To understand whether level of WP dependence influences the impact of WP flavoring on smoking behaviors, intentions for continued use, abuse liability, and exposure to tobacco-related toxicants. Compared to high dependence users smoking unflavored WP tobacco, low dependence users will show greater declines in (H2a) puff frequency and duration resulting in lower levels of smoke inhalation, (H2b) intentions of continued use, (H2c) abuse liability, and (H2d) their exposure to nicotine and CO while smoking unflavored-sweetened and unflavored-unsweetened (greatest decline) vs. flavored-sweetened WP tobacco.

[figure not shown]

Our team is uniquely suited to conduct this investigation. Understanding how WP smokers and smoking would be influenced by a flavoring ban is critically important. This novel study addresses seven of the FDA's research priorities and will contribute knowledge urgently needed by the FDA and health officials to effectively regulate WP tobacco in a way that best serves public health.

SIGNIFICANCE

The rapidly growing popularity of WP smoking: While traditional tobacco product use (cigarettes, cigars, etc.) continues to decline, WP smoking is on the rise in the United States.^{1,17} From 2011 to 2014, current (past 30-day) cigarette use declined from 15.8% to 9.2% among high school students, while during the same period, current WP use increased from 4.1% to 9.4%.¹ Additionally, WP has overtaken cigarettes as the most frequently tried tobacco product among young adults (46.6%)¹⁸ and is frequently the first tobacco product ever tried (12.0%).² Recent estimates of current and ever WP use among adults also indicates an upward trend, with current and ever use rates currently at their highest (1.5% and 9.8%, respectively).¹⁹

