WP Smoking Session Procedures: After completing the initial screening over the phone or online, participants will be informed of the study procedures and invited to the lab to complete the four WP smoking sessions. To ensure 12-hr abstinence, upon their arrival at the lab, participants will perform exhaled carbon monoxide testing (eCO<20ppm) and confirm that they have not used any nicotine/tobacco/marijuana products over the last 12 hours. Pregnancy exclusion will also be confirmed with a urine test (n.b.: pregnancy tests will be completed at each visit throughout the study). Along with a member of the study staff, the participant will review informed consent to ensure they understand their rights as a participant. Participants will be randomized and complete study procedures in self-selected dyads. The sessions will be counterbalanced and include: 1) smoking preferred flavored-sweetened WP tobacco 2) smoking unflavored-sweetened WP Tobacco and 3) smoking preferred flavored-very low sweetened WP tobacco and 4) smoking unflavored-very low sweetened WP tobacco. Participants will complete all four study visits in the laboratory. Pre-session abstinence from tobacco for at least 12 hours will be mandatory for all participants. Abstinence will be confirmed via participant self-report and an exhaled carbon monoxide monitor (< 20 ppm) for tobacco use. Participant dyads will first complete a 10-minute puffing session separated by 30-second intervals with the prepared hookah and then smoke *ad libitum* for up to 1 hour. This procedure will be completed for all visits. Participants will also complete a minimum 48-hour washout period between sessions.

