Questionnaire⁶⁷ will assess the desire and liking of all three WP tobacco products, positive and negative effects (i.e., side effects), and perceived strength and effectiveness. The *modified Cigarette Purchase Task*^{68,69} will ask participants how much they would be willing to pay (ranging from 0¢ to \$1,120) to smoke the four WP tobacco preparations (modified by substituting “1 cigarette” for “45-minute session of waterpipe smoking”), “How much would you be willing to pay for...a 45-minute session of waterpipe smoking [with the current waterpipe tobacco]?”). Willingness to spend more will indicate greater abuse liability. Smoking urges/craving will be measured using a modified version (replacing the word “cigarette” with “waterpipe”) of the *TiffanyDrobes Questionnaire of Smoking Urges: Brief Form*.⁷⁰ This is a 10-item measure where participants rate smoking-related items (“All I want right now is a cigarette.”) on a 7-point Likert scale ranging from ‘strongly agree’ to ‘strongly disagree’. Similar to previous WP studies, we will collapse the items into two previously identified factors (Factor 1: strong desire and intention to smoke; Factor 2: anticipation of relief from withdrawal symptoms). Nicotine withdrawal will be assessed using the empirically validated 15-item version of the *Minnesota Nicotine Withdrawal Scale*.⁷¹ This measure assesses smoking craving, anger/irritability, anxiety, depressed mood, restlessness/difficulty concentrating, increased appetite, sleep problems, and somatic symptoms (nausea, constipation, sore throat, dizziness, coughing). Behavioral intentions is the best proximate predictor of behavior and changes in behavioral intentions are associated with changes in related behavior.⁷² Behavioral intentions of continued WP use will be evaluated at the end of the WP session using a 4-item, 7-point Likert scale ranging from 1 (“extremely unlikely”) to 7 (“extremely likely”) where they will answer “If this was the only flavor available, how likely are you to: 1) try this product again, 2) pay to smoke this product at a waterpipe lounge/bar, 3) purchase this product for personal use, 4) use this product regularly. Other self-report measures that will be administered during the baseline, pre-session, and/or post-session visits include tobacco use and frequency, waterpipe readiness rulers, hooked on nicotine checklist, waterpipe knowledge, VAS current feelings, Cannabis Use Disorders Identification Test-Revised (CUDIT-R), and finally, adapted multiple choice procedure questions.

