Involvement and Design: Participants' eligibility will be determined over the phone or online using a screener and a pregnancy test will be completed at the initial visit to ensure that the participant is not pregnant. Those who are eligible and willing to participate will be invited to sign informed consent and complete their baseline visit. Enrolled WP smokers will complete four, 2-hr long counterbalanced WP smoking sessions that are preceded by 12 hours of overnight tobacco abstinence, biochemically verified by exhaled carbon monoxide (eCO<20ppm). Sessions will be separated by a standard 48-hour washout period. Participants will first complete a controlled 10-minute puffing session separated by 30-second intervals with the prepared hookah and then smoke ad libitum. The WP puff topography device will discretely record smoking behavior throughout the session, including puff duration, number of puffs, puff volume, and time between puffs. Blood samples (15ml per sample), eCO, and self-report measures of craving and withdrawal will be recorded immediately before and after the smoking session with two blood samples (less than 10mL) collected during the 10-minute puffing session. Self-report measures of abuse liability, as well as interest and willingness to continue to use the WP product just smoked will be assessed within 5 minutes after completing the smoking session.

Sources of Materials

All data collection will follow HIPAA guidelines. Data will be collected directly from the participant by a research assistant. Data will include participant responses to computer-based survey questionnaires and collected blood and breath samples.

Access to Identifiable Information and Data Storage: Only research assistants who have completed training in the ethical conduct of research and the study PI ([name]) will have access to individually identifiable private information about human subjects. All data will be treated as confidential and will never be stored or reported in association with identifying information. In the presence of hard copies of signed informed consent,

IRB NUMBER:

7117

IRB APPROVAL DATE:

12/18/2017

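### The intention question fixes which flavor is on sale but not which sweetener level, so the sweetener part of the intention outcome is ambiguous

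*Combined protocol and SAP*

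**What the plan says.** The Specific Aims define four sessions, "preferred flavored-sweetened, preferred flavored-very low sweetened, unflavored-sweetened, unflavored-very low sweetened", and WP Smoking Session Procedures repeats them. This is a 2 x 2 layout: flavored or unflavored, by sweetened or very low sweetened.

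Under Self-report Measures, behavioral intention "will be evaluated at the end of the WP session using a 4-item, 7-point Likert scale". The stem and first item are "If this was the only flavor available, how likely are you to: 1) try this product again". The other three items are "2) pay to smoke this product at a waterpipe lounge/bar, 3) purchase this product for personal use, 4) use this product regularly". Section 5.1 (Involvement and Design) gives the target of the measure: "interest and willingness to continue to use the WP product just smoked will be assessed within 5 minutes after completing the smoking session".

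H2b in Aim 2 predicts that low dependence users will show larger declines in intention than high dependence users "while smoking unflavored-sweetened and unflavored-unsweetened (greatest decline) vs. flavored-sweetened WP tobacco". Predicted Results orders interest in continued use across all four products. The Data Analytic Plan lists interest in continued use among the Aim 2 outcomes, modelled with a flavoring-by-dependence interaction.

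**The concern.** A stem of this kind tells the respondent what else can be bought. Here it closes the market for one of the two experimental factors and is silent on the other. After a very low sweetened session, one participant may imagine that only this preparation exists, while another may imagine that the sweetened version of the same flavor is still on the shelf. They would be answering different questions, and their scores would be averaged together.

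At stake is the sweetener component of intention. The trial has a stated interest in it: the Significance section sets the German glycerin limit (at most 5%) against US levels (about 25-50%), and links support for the hypotheses to FDA authority over glycerin sold separately. How likely people are to continue when only low-sweetener tobacco can be had is therefore a quantity a reader would want from these data.

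**Working it through.** No arithmetic on sample size, power or error rate applies. The plan's power figures are for total volume of smoke inhaled. The check is a comparison of wording.

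**1. What each session's question specifies, with *flavor* read in its ordinary sense**

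| Session | Product rated | Flavor market | Sweetener market |
|---|---|---|---|
| Preferred flavor, sweetened | this product | preferred flavor only | not stated |
| Preferred flavor, very low sweetened | this product | preferred flavor only | not stated |
| Unflavored, sweetened | this product | unflavored only | not stated |
| Unflavored, very low sweetened | this product | unflavored only | not stated |

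The rated product changes in every row. The stated market changes only with flavor. The silence matters most in the two very low sweetened rows, where the assumed alternative would be the sweetened product that the hypotheses expect to be preferred.

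**2. Three ways to read a very low sweetened session**

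- *This flavor* means the whole preparation just smoked. This is what Section 5.1 intends.
- The participant answers for the flavor in general. The sweetened and very low sweetened answers move together, and the sweetener difference shrinks.
- The participant rates this product but supposes the sweetened version is on sale. The answer drops, and the sweetener difference widens.

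The last two push in opposite directions. The documents give no basis for saying how many participants would take each reading, so neither size nor sign can be computed.

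**3. Where the sweetener step enters the hypotheses**

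Write FS, US and UV for mean intention toward the flavored-sweetened, unflavored-sweetened and unflavored-very low sweetened products. (Aim 2 calls the last one unflavored-unsweetened; I take it to be the same product.) H2b concerns the declines FS − US and FS − UV, and says the second is the greatest. The comparison between them is

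(FS − UV) − (FS − US) = US − UV,

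which is a change of sweetener with flavor held fixed. Predicted Results goes further: its ordering also places the flavored-very low sweetened product relative to the two sweetened ones.

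**4. Does any other text close the gap?**

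Section 5.1 names the product just smoked, but that text describes the measure and is not shown to participants. The purchase task under Self-report Measures asks about "a 45-minute session of waterpipe smoking [with the current waterpipe tobacco". It shows that product-level wording is already used in the same questionnaire set, but it contains no availability restriction and so is not a model of a closed market. No instruction tells participants whether a sweetened version remains available.

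**The case against.** The strongest reply is that the plan uses *flavor* broadly. The opening of the Specific Aims says added sweeteners may flavor the tobacco, the Significance section says humectants sweeten and may enhance flavor, and the Data Analytic Plan models the conditions under one main effect of flavor. On that usage, *this flavor* is the whole preparation and the stem is complete. This stands as a plausible reading, and some participants will take it. It does not make the reading uniform. Those texts are the investigators' own; participants meet the narrow sense when they choose a preferred flavor from a selection and are asked whether their first waterpipe was flavored or unflavored.

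Second, each item rates this product. That also stands, and it rules out a stronger conclusion that a reader might draw: that the outcome fails to measure intention toward the very low sweetened products, or that flavor and sweetener effects on intention cannot be ranked at all. The documents support neither. What is unclear is the set of alternatives assumed, not the object rated.

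Third, both H2b contrasts against the flavored-sweetened product include a change of flavor, the Aims name a flavoring ban as the policy question, and H2b is a difference between dependence groups. All true. A shift common to both groups would cancel from that difference, although a proportional one would not, and the documents give no reason to expect the groups to read the stem differently. This confines the problem to the sweetener step and to comparisons that rest on it.

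Finally, the plan states that all measures have been used before by the laboratory and are reliable and valid. That does not address how this stem works when sweetener is varied separately from flavor.

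**Conclusion.** The stem is ambiguous for sweetener, the second factor of the design. Intention toward each product is measured, but the sweetener component is blurred: the step behind the greatest decline in H2b, and the ordering of interest in continued use under Predicted Results. Size and direction are unknown, and no figure for either can be taken from the documents. The conclusion assumes only that some participants read *flavor* narrowly and others do not.

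The point is modest. Intention is not the primary outcome, it is listed for modelling only under Aim 2, and sample size, power and alpha are untouched. It still deserves action, because the ambiguity cannot be repaired in the analysis: nothing collected records which market each respondent had in mind.

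**What to change.** In the behavioral-intention text under Self-report Measures, and in the computer-based questionnaire, change the stem to: *If the waterpipe tobacco you just smoked was the only waterpipe tobacco available, how likely are you to:*. Keep the four items and the 1 to 7 scale as they are, and use the same stem in all four sessions. This closes the market for both factors and matches the target given in Section 5.1.

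The cost is one phrase in the questionnaire and a minor wording change for the IRB, with no added burden for participants. The small downside is a slight departure from any version of the stem the laboratory has used before. The change should be in place before the first session. The documents do not say whether enrolment has begun; if it has, the stem must not be switched within a participant, because that would mix question wording with product and period.

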Power and Data Analytic Plan: Power - Aim 1 (assumes 20% attrition of 82 participants recruited): Overall levels of smoke inhalation is our primary outcome; thus, we will estimate power based on this outcome. As no study to date has investigated the impact of WP flavoring, assumptions are based on a clinical laboratory investigation of percent changes in smokers' topography while smoking menthol vs. non-menthol cigarettes.⁷⁷ According to Chow et al.,⁷⁶ 60 WP users in a Williams 6×4 crossover design achieve >87.5% power to detect a decrease of ≥23L (or ≥20% decrease for unflavored-very low sweetened vs. flavored-sweetened) and ≥18L (unflavored-very low sweetened vs. unflavored-sweetened) in total volume of smoke inhaled using two-sided tests with 0.025 alpha level (used to adjust for the aforementioned 2 pairwise comparisons), conservatively assuming a mean total volume of 115L, 110L, 100L, and 92L for flavored-sweetened, unflavored-sweetened, flavored-very low sweetened, and unflavored-very low sweetened condition, respectively, a common standard deviation of 30L, and a within-subject correlation varying from 0.1 to 0.8. Power - Aim 2: Based on a comparison study of puff topography between high vs. low dependent WP smokers,⁶³ we assume a decrease of 10L (unflavored-very low sweetened vs. flavored-sweetened) and 5L (unflavored-very low sweetened vs. unflavored-sweetened) in total volume of smoke inhaled among high dependence WP users, and a decrease of 44L (or 40% decrease for unflavored-very low sweetened vs. flavored-sweetened) and 39L (unflavored-very low sweetened vs. unflavored-sweetened) in total volume of smoke inhaled among low dependence WP users. As in the power calculation for Aim 1, we assume a common standard deviation of 30L in total volume and a within-subject correlation varying from 0.1 to 0.8. Based on these assumptions, we estimate that 30 high dependence and 30 low dependence WP users achieve >83% power to detect the difference between high and low dependence groups in terms of Δ total volume (unflavored-very low sweetened vs. flavored-sweetened or unflavored-very low sweetened vs. unflavored-sweetened), using a two-sided, two-sample t-test with an adjusted alpha level of 0.025.

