Data Analytic Plan: Data will be summarized using mean (SD). Both overall and stratified (by dependence level) statistics will be reported. For Aim 1, we will use linear mixed effects models (with a random subject effect) to assess the main effect of flavor on total volume of smoke inhaled, abuse liability score, nicotine and CO exposure levels. In addition, period and carryover effects will be considered in the model. All pairwise comparisons for the main effect of flavor will be conducted and Bonferroni-adjusted p-values reported. For Aim 2, we will further include dependence level (high vs. low) and its interaction with flavoring in the linear mixed effects models (as in Aim 1) for outcomes including total volume of smoke inhaled, interest in continued WP use, abuse liability score, and nicotine and CO exposure levels. If the interaction term is significant, flavoring group differences in the outcome for high and low dependence subjects will be compared using contrasts, again adjusting for multiple comparisons with Bonferroni's method. Data will be transformed as appropriate. Missing data will not be imputed and likelihood based linear mixed models will yield valid statistical inference under missing at random (MAR) and ignorable missing mechanism assumptions. A two-sided p-value of <0.05 defines statistical significance. The SAS software (v9.3, Cary, NC) will be used for all data analyses.

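### The power paragraph is computed for 60 users of 82 recruited, two tests at 0.025 and a six-sequence design, whereas the plan is 76 of 94, six Bonferroni tests for Aim 1 and four conditions

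*Combined protocol and SAP*

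**What the plan says.** **Power text** (Power and Data Analytic Plan). Aim 1 opens with "Power - Aim 1 (assumes 20% attrition of 82 participants recruited" and then gives "60 WP users in a Williams 6×4 crossover design achieve >87.5% power" for decreases of 23 L and 18 L in total volume inhaled, "using two-sided tests with 0.025 alpha level (used to adjust for the aforementioned 2 pairwise comparisons". It assumes means of 115, 110, 100 and 92 L, SD 30 L and a within-subject correlation of 0.1 to 0.8. For Aim 2 it says "30 high dependence and 30 low dependence WP users achieve >83% power", by a two-sample t-test at 0.025, for the same two contrasts.

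**Planned size.** Specific Aims: "76 current WP smokers (38 low dependent, 38 high dependent) will complete four counterbalanced WP smoking sessions". Participants: 94 recruited, 47 per group, to give 76 completers after 20% attrition. Recruitment Feasibility and Retention repeats 94.

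**Planned analysis** (Data Analytic Plan). Aim 1: "All pairwise comparisons for the main effect of flavor will be conducted and Bonferroni-adjusted p-values reported". For Aim 2, if the interaction is significant, group differences "will be compared using contrasts, again adjusting for multiple comparisons"; the number of contrasts is not given. It also says that "period and carryover effects will be considered in the model".

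**The concern.** A power statement should describe the trial that will be run and the tests that will be done. This one differs in four places: analysed number, recruited number, alpha, and the sequence set. It also fails on its own terms, because 82 less 20% is about 66, not 60.

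Two things are at stake. A reader who takes the paragraph at face value would think that 60 completers give 87.5% power for the primary outcome, and under the planned six tests that is not so across the whole stated correlation range. And the only place that names a sequence set names one that cannot be period-balanced for four conditions.

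**Working it through.** **Inputs.** SD 30 L, correlation rho 0.1 (the low end, hence the worst case), differences of 18 L and 23 L, and the Aim 2 decreases all come from the power paragraph. The planned 76 and 38+38 come from Specific Aims, and the six pairs from the Data Analytic Plan. Participants are treated as independent.

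**SD of a within-person difference:** 30 × √(2 × (1 − 0.1)) = 40.25 L.

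**1. Reproduce the printed Aim 1 figure.** n = 60, alpha 0.025:
- SE = 40.25/√60 = 5.196 L. Non-centrality for 18 L = 18/5.196 = 3.464.
- Paired t, 59 df: 87.5% (87.46%). Mixed-model residual df, 3n − 6 = 174: 88.4%. Normal approximation: 88.9%.
- For 23 L: 98.2% to 98.6% across the three methods.

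The printed 87.5% is reproduced.

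**2. Reproduce the printed Aim 2 figure.** The difference between groups is 44 − 10 = 34 L for one contrast and 39 − 5 = 34 L for the other. With 30+30, SE = 40.25 × √(2/30) = 10.39 L, and 34/10.39 = 3.27. Two-sample t at 0.025: 83.1%. Reproduced.

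**3. Attrition.** 82 × 0.8 = 65.6, and 60 of 82 would be 26.8% attrition. By contrast 94 × 0.8 = 75.2, which fits 76.

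**4. Number of tests.** Four conditions give 4 × 3/2 = 6 pairs, so Bonferroni alpha is 0.05/6 = 0.0083.

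**5. Aim 1 power under the planned alpha, rho 0.1:**

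| n | alpha | 18 L, paired t | 18 L, mixed-model df | 23 L, paired t |
|---|---|---|---|---|
| 60 | 0.025 | 87.5% | 88.4% | 98.2% |
| 60 | 0.05/6 | 76.5% | 78.6% | 95.1% |
| 76 | 0.05/6 | 87.9% | 89.1% | 98.7% |
| 76 | 0.025 | 94.4% | 94.9% | 99.6% |

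With n = 60 and alpha 0.05/6, 18 L power passes 87.5% once rho exceeds about 0.29 by the paired t, or about 0.26 with mixed-model df.

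**6. Carryover.** In a four-sequence Williams square, fitting first-order carryover raises the variance of a treatment contrast by 0.55/0.50 = 1.10. With n = 76 and 0.05/6, the 18 L non-centrality falls from 3.899 to 3.899/√1.10 = 3.717. Power is then 83.9% for 18 L and 97.7% for 23 L (paired t).

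**7. Aim 2 at 38+38, rho 0.1.** SE = 40.25 × √(2/38) = 9.23 L, and 34/9.23 = 3.68. Power by number of contrasts: two (0.025) 91.6%, three (0.0167) 88.8%, six (0.0083) 83.1%.

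**8. Sequences.** Read as six sequences by four periods, each condition would have to appear 6/4 = 1.5 times per period, which is impossible. Specific Aims, Design Overview and WP Smoking Session Procedures all say that sessions are counterbalanced, but none gives a sequence set.

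**The case against.** The strongest reply is that nothing is lost. The other sections consistently plan 76 of 94, and at 76 the printed levels hold even at 0.05/6. The paragraph reports power at 60; it does not say that 60 is enough. Powering on 60 when 66 are expected is, taken alone, cautious. The shortfall at 60 needs the low end of the correlation range. Most of this stands, and it limits the finding to a wrong justification. It does not remove the contradiction on size and alpha, which no section resolves.

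Four stronger readings are tempting but unsupported:
- **The trial is underpowered.** Not for the two named contrasts at the planned size.
- **Aim 2 also has six tests, and so only 70.4% power with 30+30.** The Data Analytic Plan gives no count for Aim 2 and the power text names two contrasts. The 70.4% needs both the unplanned 30+30 and an assumed six.
- **Condition will be confounded with period.** The label appears once, in a power calculation. No six-sequence randomization list is shown, and sessions are said to be counterbalanced. Unequal placement with period in the model would cost precision and would not by itself bias the contrasts.
- **Self-selected dyads pull power below these levels.** The documents give no within-dyad correlation and do not say clearly whether both members are analysed, so no figure can be derived from them.

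The plan also claims no power for the four smaller pairwise differences, so their lower power does not contradict the paragraph.

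**Conclusion.** The concern holds as an inconsistency that should be corrected. The power paragraph's analysed number, recruitment figure, group sizes and Aim 1 alpha are not those of the planned trial, and its design label does not fit four counterbalanced conditions.

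At rho 0.1, the 60 users it cites give 76.5% to 78.6% for 18 L under the planned six tests, against more than 87.5% stated. The planned 76 give 87.9% to 89.1% for 18 L and about 99% for 23 L. The margin for 18 L is thin: by the paired t it is 0.4 points (87.9 − 87.5), and fitting carryover terms, which the plan only says it will consider, lowers the figure to about 84%.

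These results rest on the paragraph's own SD and correlation range, on independent participants, and on 76 completers. Confidence is high for the size and Aim 1 alpha mismatches. For Aim 2 the alpha question stays open until the number of contrasts is stated.

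**What to change.** 1. **Sizes.** In the power text, replace 60 of 82 with 76 of 94, and 30+30 with 38+38.
2. **Alpha, Aim 1.** Make the power text and the Data Analytic Plan agree, in one of two ways. Either restate power at 0.05/6 (about 88% for 18 L and 99% for 23 L at rho 0.1; about 84% and 98% if carryover terms are fitted). Or name the two contrasts as primary in the Data Analytic Plan at 0.025 each (94.4% and 99.6%, without carryover terms) and label the other four pairs secondary.
3. **Alpha, Aim 2.** State the same number of contrasts in both places and quote the matching power at 38+38 and rho 0.1: 91.6% for the two already named, or 83.1% if six are meant.
4. **Sequences.** Replace the 6×4 label with a set balanced for four conditions over four periods, for example a four-sequence Williams square, and check that the randomization list uses it.

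The cost is protocol wording and one check of the randomization list, which would have to be rebuilt only if it is not balanced. Enrolment stays at 94.
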